8.4.2.2 SAE Information to Report

All information available regarding an SAE must be submitted in the timeframes indicated. At a minimum, SAE reports must contain the subject ID, the SAE verbatim term, onset date, relationship to study drug/causality, and a brief narrative of the event. Please note that **relationship to study drug/causality as well as the reported verbatim term are very important** and should be included in the initial report as it may impact expedited regulatory reporting requirements for the event. The date of SAE discovery by the site staff should be documented in the source documents.

The investigator must record all relevant information regarding an AE/SAE in the applicable sections of the CRF. It is not acceptable for the investigator to send photocopies of the subject's medical records in lieu of completion of the appropriate AE/SAE pages. However, there may be instances when copies of medical records for certain cases are requested by the CRO and/or the Sponsor. If medical records are submitted to the CRO then all subject personal identifiers must be completely and thoroughly redacted prior to submission.

A blank SAE Report Form and instructions for SAE reporting will be provided to the site and will be maintained in the investigator's study file. The SAE Report Form must be completed and emailed to [contact] according to the timeframes specified in [Section 8.4.2.1](#). The SAE Report Form should include copies of relevant source documents, if applicable. Reconciliation of any discrepancy noted during monitoring and amending the eCRF is required.

If new information about an SAE is received or corrections to data are needed, the investigator should complete a new SAE Report Form and check the "follow-up" box on the form. This follow-up SAE Report Form should be submitted within 24 hours of learning of the information, especially if the new information concerns seriousness, relatedness, or the event term of an AE.

Sites acting under their local IRB/IEC should submit all applicable events, unanticipated problems, and safety reports to the site's local IRB/IEC, if applicable. All safety reporting deviations should also be submitted to their local IRB/IEC, if applicable.

8.4.3 ADVERSE EVENTS OF SPECIAL INTEREST

Please note that for an event to be classified as an AE of special interest (AESI), the event should meet the definition of an Adverse Event per [Section 8.1.1](#). Thus, if the investigator considers the event to be an AE, and it meets one or more of the criteria listed below, then the event should be classified as an AESI and

reported according to the timeframe specified.

The following will be considered AEs of special interest (AESI) if they qualify as AEs per the preceding paragraph:

- Clinically significant peripheral edema or pulmonary edema.
- Clinically significant systolic BP >160 but <170 mmHg over consecutive timepoints spanning 30 or more minutes.
- Clinically significant systolic BP <90 or >170 mmHg at a single timepoint.
- Clinically significant diastolic BP >100 but <110 mmHg over consecutive timepoints spanning 30 or more minutes.
- Clinically significant diastolic BP <60 or >110 at a single timepoint.
- A change of >25% from baseline in systolic and/or diastolic BP.
- Reduced kidney function (eGFR < 45 mL/min/1.73 m²).
- Suspected transmission of blood-borne infectious agents.

AESI occurring during the study should be reported within 48 hours of observation or learning of the event, unless the event is serious, in which case the event must be reported according to the timeframes specified in [Section 8.4.2.1](#).

Note: Blood pressures meeting the parameters above that are not considered adverse events need not be reported within the 48-hour window. Rather, these will be considered “blood pressures of special interest” and analyzed separately.

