2.3 POTENTIAL RISKS AND BENEFITS

2.3.1 KNOWN POTENTIAL RISKS

Human plasma is used as a therapeutic product (Burnouf 2007) and serves as the source material for manufacturing plasma-derived therapeutic products via fractionation, including GRF6021. GRF6021 is a human [REDACTED] fraction [REDACTED] and serves as a viable source of soluble, infusible plasma proteins from healthy male and female donors. It has been [REDACTED] [REDACTED].

GRF6021 has two Important Identified Risks (Hypersensitivity reactions including anaphylaxis and Hypotension and allergic reactions) and one Important Potential Risk (transmission of pathogens).

The overall reporting frequency for hypersensitivity reactions was 0.001% (PSUR). Several steps have been implemented in this study to minimize this risk, including dosing under medical supervision in facilities with adequately trained personnel, access to subcutaneous epinephrine, frequent vital sign measurements during and after each infusion, a 4-hour safety-monitoring period after the end of each infusion, and the exclusion of subjects with a history of allergic reactions to any blood product or IV infusions. In addition, because monitoring beyond the 4-hour period may be required in some cases, all participating study sites will have inpatient facilities available for overnight observation or the ability to transfer the subject to such a facility.

The overall reporting frequency for hypotensive events was 0.002% (PSUR). Several steps have been implemented to minimize this risk, including a slow infusion rate with stepwise increase in rate that can be adjusted to tolerability; frequent monitoring of blood pressure during and after each infusion, guidance on what action to take based on observed changes in blood pressure, and exclusion of subjects with symptomatic orthostatic hypotension. Hypotension is most likely to occur following rapid infusion or intraarterial administration to patients on cardiopulmonary bypass. GRF6021 is contraindicated for use in patients on cardiopulmonary bypass as severe hypotension has been reported [REDACTED] and these subjects are excluded in this study. In the instance of a hypotensive episode, the blood pressure may normalize spontaneously after the slowing or discontinuation of the infusion. If necessary, vasopressors can also be used to correct the hypotension (PI).

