8.5 STUDY HALTING RULES

If any of the following safety events occur, a Safety Evaluation Meeting (defined below) will be triggered:

- Three or more SAEs in the same SOC that are assessed as possibly or definitely related to the study agent by the investigator and confirmed as such by the Sponsor (see [Section 8.2.2 Relationship to Study Agent](#)).
- Within or between any of the dosing groups: an overall pattern of symptomatic, clinical, or laboratory events associated with the study agent that the Sponsor's Program Physician or designee consider a serious potential safety concern (e.g., suspicious overall pattern).

Events that are more likely related to the infusion procedure, such as infiltration or hematoma, will not be considered “drug related” and will not contribute to the count of definitely-related SAEs that would trigger a Safety Evaluation Meeting.

Safety Evaluation Meeting

If safety events of potential concern occur during the trial (i.e., 3 related events in the same SOC or a suspicious overall pattern, as defined above) a Safety Evaluation Meeting will be triggered, and dosing may be temporarily halted based on the observations. The Sponsor will inform investigators, FDA, ANSM, and TGA in the event of any temporary halt in dosing at any time during the conduct of the study. The purpose of the meeting is for investigators, the Sponsor, and the CRO Medical Monitor(s) to discuss and evaluate the safety of the subjects using available aggregated safety data and without compromising study blinding, unless the Sponsor deems unblinding necessary for safety evaluation.

Attendants at the Safety Evaluation Meeting will include the Program Physician of Alkahest (or his/her designee), the CRO medical monitor(s), and available active investigators participating in the trial. Such a meeting may also include external consultants with expertise relevant to the specific safety signal(s) detected. After sufficient data review, the Sponsor will choose one of the following courses of action:

1. Continue dosing with no change to protocol.
2. Halt dosing in all groups and stop the study.
3. Continue with a modified protocol design and amend the protocol as appropriate.

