6. MONITORING FOR ADVERSE REACTIONS

Throughout the infusion, the blinded Outcomes Assessor or designee should continuously assess the subject for signs of AEs.

In the event of an AE, the PI or designee physician should be notified, and the event should be recorded for later transcription into the CRF. The PI should assess immediately whether an AE is an AE of special interest and/or an SAE and report it accordingly, as per the protocol.

Table 3. Recommended AE Actions for PI or Physician Designee

Mild Events	

 • Body temperature >38.0°C (>100.4°F) but <39.0°C (<102.2° F) • Chills • Dizziness • Fatigue • Flushing • Mild-to-moderate itching • Redness of skin or rash • Urticaria (hives) in the absence of any other sign of symptom • Nausea / Vomiting 	
Stop the infusion, recheck vital signs, and notify the PI or physician designee. After assessment by a physician and consideration of treatment of fever with acetaminophen (if applicable), the unblinded Infusion Nurse may restart the infusion rate at half the rate at the onset of the infusion event and maintain the reduced rate for at least 30 minutes. If this rate is tolerated, the unblinded Infusion Nurse may increase the rate as tolerated by 30 mL per hour (0.5 mL/min) every 30 minutes (± 5 minutes) as tolerated.

Moderate to Severe Events	

 • Bronchospasm (wheezing, coughing) • Hoarseness or other signs of laryngeal edema • Throat or mouth pain or irritation • Chest pain/back pain • Shortness of breath • Fever ≥39 °C (102.2° F) • Rigors • Hemoglobinuria • Oliguria • Sustained hypertension (systolic BP (SBP) >170 and/or diastolic BP (DBP) >100 not present before the first infusion) • Sustained hypotension (SBP <90 and/or DBP <50 not present before the first infusion) • Tachycardia (HR>100 bpm) • Signs / symptoms of volume overload 	
Stop the infusion, recheck vital signs, and notify the PI or physician designee. The PI or physician designee should administer appropriate supportive treatment, as necessary. The infusion should not be restarted, and the subject should not be dosed further. Notify the Medical Monitor(s) as soon as possible (preferably by end of business day).

Life-Threatening Events	

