9.1.3. Other Significant Adverse Events

AEs of special interest (AESI) are defined in the protocol. These are to be considered as Adverse Events by the PI in order to be recorded:

A summary tabulating these criteria for safety will be presented by SOC, PT, and treatment group. All AESIs will be flagged in the AE listings.

Adverse events with preferred terms associated with blood pressure changes will also be presented by infusion period, SOC, PT, and treatment group. Infusion period will be further categorized by whether the event start date occurred during the infusion period or after the infusion period. Examples of such events can be identified by the following preferred terms: blood pressure decreased, blood pressure diastolic decreased, blood pressure systolic decreased, blood pressure increased, increased blood pressure, blood pressure diastolic increased, blood pressure systolic increased, hypotension, hypertension, low blood pressure, high blood pressure. This is a non-exhaustive list and a review of AE MedDRA coding will be conducted prior to lock to identify all events associated with blood pressure changes.

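### Hypersensitivity and allergic reactions are named among the Important Identified Risks but have no AESI entry and no grouped table by arm or infusion period

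*Protocol*

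**What the plan says.** Protocol 2.3.1 states the product's known risks: "GRF6021 has two Important Identified Risks (Hypersensitivity reactions including anaphylaxis and Hypotension and allergic reactions) and one Important Potential Risk (transmission of pathogens". Allergic reactions appear twice in effect, once as the first identified risk and once attached to hypotension.

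Protocol 8.4.3 defines AESIs by a list introduced with "The following will be considered AEs of special interest (AESI) if they qualify as AEs per the preceding paragraph". Two of the named risks can be recognised in it: hypotension through criteria such as "Clinically significant systolic BP <90 or >170 mmHg at a single timepoint", and pathogens through "Suspected transmission of blood-borne infectious agents". The other items are edema, further blood pressure criteria and reduced eGFR. A non-serious AESI must be reported within 48 hours.

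SAP 9.1.3 takes the AESI definition from the protocol and adds one grouped display: "Adverse events with preferred terms associated with blood pressure changes will also be presented by infusion period, SOC, PT, and treatment group". That display is Table 14.3.2.4. Its term list is open-ended and is to be completed by a coding review before lock.

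Protocol Appendix 11, section 6, Table 3 shows that allergic-type signs are anticipated during infusions. Its mild tier includes itching, rash, flushing and "Urticaria (hives) in the absence of any other sign of symptom". Its moderate-to-severe tier includes bronchospasm and signs of laryngeal edema. Anaphylaxis has its own tier.

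**The concern.** Safety and tolerability is the primary objective, so the outputs should answer directly for each risk the protocol itself names. For hypotension, the reader gets AESI reporting, an AESI table and a blood pressure table split by infusion period. For hypersensitivity, the reader gets individual preferred terms and must decide which belong together.

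The split by infusion period matters because each subject is exposed twice, at Weeks 1 and 13. Whether allergic-type events differ between arms, or between first exposure and re-exposure, is an obvious question for a plasma protein product, and no planned table addresses it. Subjects may also go home after the 4-hour observation period, so a later mild reaction may first be noted away from the site.

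**Working it through.** **1. Named risks against planned handling.**

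| Risk in Protocol 2.3.1 | Stated frequency | Item in 8.4.3 | Grouped table in SAP |
|---|---|---|---|
| Hypersensitivity including anaphylaxis; allergic reactions | 0.001% | none | none |
| Hypotension | 0.002% | yes, within 5 BP items | Table 14.3.2.4 |
| Pathogen transmission | 0.002% | yes, 1 item | AESI table only |

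The eight AESI items are 1 edema + 5 blood pressure + 1 eGFR + 1 blood-borne infection. None is allergic.

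**2. Does rarity explain the gap?** The protocol says "The overall reporting frequency for hypersensitivity reactions was 0.001% (PSUR"). The other two risks, at 0.002%, are of the same order and are on the list. The documents give no reason for treating them differently.

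**3. Planned AE summary tables.** Tables 14.3.1.1 to 14.3.1.4 and 14.3.2.1 to 14.3.2.4 make eight. They cover an overall summary, SOC/PT, severity, relationship, withdrawal, seriousness, AESI and blood pressure terms. None forms an allergic group.

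**4. The plan's own safety figure.** Protocol 10.5 and SAP 3.2 give an upper 95% bound of about 5% for an unobserved AE in 60 active subjects. This reproduces: 3/60 = 5.0%; exact one-sided, 1 − 0.05^(1/60) = 4.87%. The bound applies to one defined event. To apply it to hypersensitivity, someone must first say which terms make up that event.

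**5. Why term rows do not give the group count.** A subject with two different terms is counted in both rows. The number with any allergic-type event therefore lies between the largest row and the sum of the rows. With three rows of about two subjects each (the size expected in step 6), that is 2 to 6 of 60, or 3.3% to 10.0%.

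**6. Illustration of visibility.** The rates here are assumed; the documents give none for solicited allergic-type events. Let a proportion T of 60 active subjects have at least one such event, split equally and independently over k terms. Each term then has rate p = 1 − (1 − T)^(1/k). With q = P(at least 3 subjects in a given row), the chance that some row reaches 3 is 1 − (1 − q)^k.

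| T | k | Expected per row (60p) | q, a given row | Some row |
|---|---|---|---|---|
| 10% | 1 (grouped) | 6.0 | 94.7% | 94.7% |
| 10% | 3 | 2.07 | 34.3% | 1 − 0.657³ ≈ 72% |
| 10% | 5 | 1.25 | 13.0% | 1 − 0.870⁵ ≈ 50% |
| 20% | 1 (grouped) | 12.0 | about 100% | about 100% |
| 20% | 3 | 4.30 | 81.3% | 1 − 0.187³ ≈ 99% |
| 20% | 5 | 2.62 | 49.0% | 1 − 0.510⁵ ≈ 97% |

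At a moderate rate, grouping makes a cluster easier to see. At a high rate it would show in the term rows anyway.

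**The case against.** The safeguards are real. Serious reactions go to the sponsor within 24 hours (8.4.2.1). Appendix 11 Table 3 stops the infusion and brings in the investigator or a physician designee even for mild signs. It also sends moderate-to-severe events to the Medical Monitor, preferably the same business day, which is faster than 48 hours. Protocol 8.6 provides cumulative AE review throughout. Protocol 8.4.1 asks for the diagnosis rather than its signs, which moves k towards 1 wherever a reaction is diagnosed. Related TEAEs and AEs leading to withdrawal are tabulated by arm. All of this stands and limits the weight of the point.

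The data are also all there, so a grouped count could be built later. That is true, but SAP section 1 would label it post hoc, and its terms could then be chosen with the arms known.

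It may also be said that the table would be empty. If 0.001% applied per infusion, the chance of any event in 60 × 10 = 600 active infusions would be 1 − (1 − 0.00001)^600 = 0.6%. For hypotension at 0.002% it would be about 1.2%, and hypotension still has both an AESI entry and a table. These are reporting frequencies, not rates under solicited collection.

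Three stronger readings are tempting and not supported.
- A reader might infer that the halting rules in 8.5 cannot see scattered reactions, because one trigger is "Three or more SAEs in the same SOC that are assessed as possibly or definitely related to the study agent by the investigator". The second trigger, a judged overall pattern, is limited neither by SOC nor to serious events. The documents also do not say which SOC any of these signs would code to.
- A reader might infer that hypersensitivity is the foremost risk because it is named first. Its stated frequency is the lowest of the three.
- A reader might infer that no allergic reaction could enter the AESI table. One with qualifying blood pressure change or edema would.

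**Conclusion.** The point holds as a mismatch between Protocol 2.3.1 and 8.4.3 that the SAP does not repair. One of the two Important Identified Risks, and the allergic part of the other, has none of the eight AESI items and no grouped table. The practical loss is narrow: no 48-hour AESI report for non-serious reactions that miss the blood pressure and edema criteria, and no prespecified count of affected subjects by arm or infusion period. The structural finding rests on unredacted text and needs no assumption about rates. Only the visibility illustration does, and it shows a modest gain. It is not a failure of subject protection or data capture. This is a cheap improvement to how the trial answers its primary question.

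**What to change.** - **Protocol 8.4.3:** reconcile the list with 2.3.1 by adding hypersensitivity/allergic reaction, including anaphylaxis.
- **SAP 9.1.3:** prespecify a hypersensitivity/anaphylaxis term list. The signs in Appendix 11 Table 3 are a natural starting point. Complete it in the same pre-lock coding review as the blood pressure list, by staff blind to allocation. The interim safety tables were produced by arm, so those settling the list should preferably not have seen them.
- **SAP tables:** tabulate that list by arm and infusion period in the Table 14.3.2.4 shell, counting each subject once for the group as a whole as well as by term.

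Protocol 8.5 is left as it stands. The cost is one line, one term list, one table on an existing shell, and some extra 48-hour reports of mild skin reactions. The table uses data already collected, so it is worth adding even if little dosing remains.

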9.3. Vital Signs

Descriptive summaries of actual values and changes from baseline will be calculated for seated systolic blood pressure, standing systolic blood pressure, and supine systolic blood pressure, seated diastolic blood pressure, standing diastolic blood pressure, and supine diastolic blood pressure, heart rate, respiration rate, and body temperature. These summaries will be presented by visit and treatment group. Vital signs are collected at all study visits. During the infusion periods (Visit 3-Visit 7 and Visit 11- Visit 15), orthostatic vital signs (supine systolic and supine diastolic blood pressure compared to standing systolic and standing diastolic blood pressure) should be measured prior to infusion start and at approximately [REDACTED] after infusion start. Seated systolic and seated diastolic blood pressure is measured at multiple timepoints during and after each infusion. Abnormal vital sign values will be flagged in the listings. Abnormal vital sign values are as follows:

- Seated systolic blood pressure value < 90 mmHg
- Seated systolic blood pressure value > 180 mmHg
- Seated diastolic blood pressure value < 50 mmHg
- Seated diastolic blood pressure value > 110 mmHg
- Incidence of orthostatic hypotension (a decrease in systolic blood pressure of > 20 mm Hg and/or a decrease in diastolic blood pressure of > 10 mm Hg between supine and standing)
- Heart rate > 100 beats per minute
- Temperature > 37.5°C
- Temperature < 36.5°C
- Respiration rate > 20 breaths per minute
- Respiration rate < 12 breaths per minute

The vital sign measurements that meet the criteria for blood pressures of special interest (listed below) will also be identified from the vital signs source data and summarized separately by study visit, timepoint, and treatment.

- Seated systolic blood pressure >180 mmHg
- Seated systolic blood pressure > 200 mmHg
- Seated systolic blood pressure < 90 mmHg
- Seated diastolic blood pressure > 110 mmHg
- Seated diastolic blood pressure > 120 mmHg
- Seated diastolic blood pressure < 50 mmHg
- A change of $\geq 30\%$ from baseline in seated systolic and/or seated diastolic blood pressure

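### Protocol 8.4.3 leaves exactly 170 mmHg systolic and exactly 110 mmHg diastolic outside both absolute AESI criteria, so some adverse events at those values lose AESI status and the 48-hour report

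*Protocol*

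**What the plan says.** Protocol section 8.4.3 lists five blood-pressure criteria among its AESI definitions:

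- Systolic, sustained: "Clinically significant systolic BP >160 but <170 mmHg over consecutive timepoints spanning 30 or more minutes".
- Systolic, single reading: "Clinically significant systolic BP <90 or >170 mmHg at a single timepoint".
- Diastolic, sustained: "Clinically significant diastolic BP >100 but <110 mmHg over consecutive timepoints spanning 30 or more minutes".
- Diastolic, single reading: "Clinically significant diastolic BP <60 or >110 at a single timepoint".
- Relative change: "A change of >25% from baseline in systolic and/or diastolic BP". This one has no duration condition and no clinical-significance qualifier.

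Entry to the list is conditional. An event is an AESI "if the investigator considers the event to be an AE, and it meets one or more of the criteria listed below". AESIs are reported within 48 hours unless they are serious, in which case the SAE timelines apply. A closing note deals with readings that are not adverse events: "Blood pressures meeting the parameters above that are not considered adverse events need not be reported within the 48-hour window". The protocol calls these blood pressures of special interest.

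SAP section 9.1.3 takes the AESI definition from the protocol and tabulates AESIs by SOC, PT and treatment. SAP section 9.3 defines blood pressures of special interest with its own limits; the lowest high-systolic limit is "Seated systolic blood pressure >180 mmHg".

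**The concern.** The two systolic bullets read as two tiers: a moderate rise must persist, and a larger rise counts at once. The diastolic bullets repeat the pattern. In each pair the lower tier stops just below the dividing value and the upper tier starts just above it, so the dividing value belongs to neither. A higher pressure can then be classed as less notable than a lower one, and a boundary reading in the middle of an episode can disqualify the readings around it.

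Nothing in the protocol suggests that 170 or 110 was meant to be exempt. The version 4.0 change log gives clarification of the blood-pressure specifications as the reason for revising these criteria. Safety is the primary objective, there is no data safety monitoring board, and AESI status is what starts the 48-hour report. Seated pressure is also taken often: every 15 minutes in the first hour of each infusion, then every 30 minutes until 4 hours after it ends, over ten planned infusions.

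**Working it through.** There is no stated figure to reproduce. The check applies the inequalities literally.

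**Step 1: absolute criteria alone.** Every integer from 161 to 200 systolic was tested against (160 < x < 170) or (x > 170), and every integer from 101 to 140 diastolic against (100 < x < 110) or (x > 110). Exactly one value is uncovered in each range: 170 and 110.

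**Step 2: broken runs.** Take half-hourly readings of 168, 170, 168. No two consecutive readings lie strictly between 160 and 170, so no run spans 30 minutes, and no reading exceeds 170. Neither absolute criterion is met. Half-hourly readings of 162, 164 meet the sustained one.

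**Step 3: the relative-change criterion.** A reading x exceeds a 25% rise when x / baseline > 1.25, that is, when baseline < x / 1.25.

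- Systolic: 170 / 1.25 = 136.
- Diastolic: 110 / 1.25 = 88.

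| Baseline systolic | Rise to 170 | Sustained 162 | Exactly 170 | 171 |
|---|---|---|---|---|
| 130 | 40/130 = 30.8% | captured | captured (>25%) | captured |
| 135 | 35/135 = 25.9% | captured | captured (>25%) | captured |
| 136 | 34/136 = 25.0% | captured | not captured | captured |
| 140 | 30/140 = 21.4% | captured | not captured | captured |
| 159 | 11/159 = 6.9% | captured | not captured | captured |

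Diastolic behaves the same way. At baseline 87 the rise to 110 is 23/87 = 26.4%, which is captured. At 88 it is 22/88 = 25.0% and at 99 it is 11/99 = 11.1%, neither of which is captured, although a sustained 102 is. Captured here means that a numerical criterion is met; clinical significance (for the absolute bullets) and adverse-event status are still required.

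**Step 4: are such baselines eligible?** Exclusion 9 concerns pressures of 160/100 or higher despite treatment, so it leaves systolic baselines of 136 to 159 and diastolic baselines of 88 to 99 possible. Exclusion 10 also removes supine diastolic above 90. It does not cap seated diastolic pressure, but it should thin out the high diastolic baselines.

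**Step 5: does another provision close the gap?** For systolic, no. The Infusion Administration Manual (Protocol Appendix 11, Table 3) lists sustained systolic pressure above 170, which again omits 170 itself. For diastolic, partly. The same row lists sustained diastolic pressure above 100 that was not present before the first infusion, and asks for notification of the Medical Monitor.

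**Step 6: how often?** The documents give no distribution of readings, so only an assumption-dependent range is possible. The simulation used 200,000 episodes per setting, true mean systolic pressure 166 to 170, reading SD 3 and baseline 136 or more. The figures are the share of episodes that a gap-free rule would capture but the written rule misses.

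| Recording assumption | Three half-hourly readings | Five half-hourly readings |
|---|---|---|
| To 1 mmHg | 5–8% | under 1% |
| To 2 mmHg | 12–18% | 3–4.5% |
| To 2 mmHg, 20% of readings rounded to the nearest 10 | 24–34% | 9–15% |

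At a baseline of 135 or lower the share is zero. These are shares of episodes already assumed to sit close to 170. They are not expected rates in this trial.

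**The case against.** The strongest reply is that almost nothing is lost. An AESI must first be an adverse event, so an adverse event at exactly 170 is entered in the CRF, coded, counted in the TEAE analysis that forms the primary endpoint and, if coded to a blood-pressure term, shown in the separate table planned in SAP section 9.1.3. SAE timelines do not depend on AESI status. The Medical Monitor and the sponsor's physician review vital-sign data throughout. All of this stands, and it is why the point is minor.

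Three stronger readings are tempting, and the documents do not support them.

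- **Any sustained 170 escapes while any sustained 162 is caught.** This overlooks the relative-change criterion in the same list, which takes in 170 at every baseline below 136 and 110 at every baseline below 88.
- **The gap carries into the counts of blood pressures of special interest.** The protocol's note does point to the same parameters, but the planned summary follows SAP section 9.3: seated systolic above 180, above 200 or below 90; seated diastolic above 110, above 120 or below 50; or a change of at least 30%. That list has no 170 limit and no sustained tier. The difference between the two documents is a separate matter.
- **The bounds need correcting in analysis programs.** AESIs are described as events the investigator records. Neither document describes deriving them from vital-sign data.

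The simulated shares are also open to challenge, because the SD, recording grid and rounding share are all assumed. The conclusion does not rest on them.

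What the reply leaves untouched is the classification itself. The text excludes a value that both neighbouring tiers imply should count, and for systolic pressure no other provision picks it up.

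**Conclusion.** The gap is certain on the wording, and its reach is narrow. It affects adverse events that are clinically significant, involve a reading of exactly 170 systolic or exactly 110 diastolic (alone or within a run near that value), meet no other listed criterion, and occur in subjects with baseline at or above 136 systolic or 88 diastolic. For those events the AESI flag and the 48-hour report are lost, and the AESI table inherits the omission. The primary TEAE and SAE analysis does not change. Diastolic exposure is smaller than systolic, because of the supine diastolic exclusion and the infusion manual's limit of 100.

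Two assumptions matter. The inequalities are taken literally; an investigator might treat 170 as qualifying anyway, but sites could then differ. Section 8.4.3 does not say which reading is the baseline for the 25% change; the limits of 136 and 88 apply to whichever reading is used. Severity: minor.

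**What to change.** Reconcile each pair of bullets in Protocol section 8.4.3 so that every systolic value above 160 and every diastolic value above 100 falls in at least one criterion. One inclusive bound at 170 and one at 110 is enough: repeating Step 1 with that change leaves no integer uncovered in either range. Add wording so that a reading at the boundary does not interrupt a sustained run. Whether the exact value belongs to the sustained or the single-timepoint bullet is a clinical choice for the sponsor, and none is proposed here.

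The change is one symbol in each of two bullets plus a short clarification about runs, communicated to sites. The cost may be a few more AESI reports. This point requires no change to the SAP's limits for blood pressures of special interest.
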